11.10.1 Reporting of Study Pausing

If a pausing requirement is met, a description of the event(s) or safety issue will be reported by the PI or Site Investigator within one business day to the IND sponsor by fax or email. The site investigator will inform the LMIV PI, the ISM, and the local IRB that a pausing rule has been met according to their requirements. The LMIV PI will notify the NIAID IRB. The IND sponsor will notify the DSMB as well as all sites conducting Sanaria-sponsored studies, or studies using Sanaria related products that the study has been paused.

11.10.2 Resumption of a Paused Study

The IND sponsor, in collaboration with the PI and DSMB will determine if it is safe to resume the study. The IND sponsor will notify the site investigators of this decision. The conditions for resumption of the study will be defined in this notification. The site investigator will notify their local IRB(s) of the study pause and of the decision to resume the study.

11.11 Pausing Criteria for a Subject

The decision to suspend administration of the study agent(s) for a single subject or for all subjects in a specific group requires discontinuation of use of the study agent to any study subject(s) until a decision is made whether or not to continue study agent in the study.

The pausing criteria for a single subject or for the subjects in this study include:

- A subject experiences an SAE or ≥ 2 or more Grade 3 or greater AE (excluding laboratory assays) that is unexpected (as determined by the IND sponsor) and is possibly, probably, or definitely related to the study agent;
OR
- Any safety issue that the Site Investigator determines should pause administration of the study agent to a single subject.

The IND sponsor, in collaboration with the PI, may also pause for an individual subject if a safety concern is identified during routine aggregate data analysis.

11.11.1 Reporting of Pausing for a Subject

If a pausing requirement is met, a description of the AE(s) or safety issue must be reported by the site Investigator by fax or email within one business day to the IND sponsor and LMIV PI. The

PIs will notify the ISM, and the local IRB (NIAID IRB, FMPOS EC). The IND sponsor will report this to the DSMB.

11.11.2 Resumption of a Paused Subject

The IND sponsor in collaboration with the PI and the DSMB will determine if it is safe to resume administration of the study agent to the subject. The IND sponsor will notify the Site investigators of this decision. The site investigators will notify their local IRB(s) of the decision to resume administration of the study agent prior to resumption.

11.12 Discontinuation of Study

Sanaria, Inc. as the study sponsor, the NIAID IRB, FMPOS EC, and the FDA may terminate this study at any time. Reasons for terminating the study may include, but are not limited to, the following:

- The incidence or severity of an AE in this or other studies indicates a potential health hazard to subjects
- Subject enrollment is unsatisfactory
- Data recording is inaccurate or incomplete
- Investigators do not adhere to the protocol or applicable regulatory guidelines in conducting the study

11.13 Withdrawal of an Individual Subject

A subject will not be considered to have completed the trial if any of the following reasons apply:

1. *Research terminated by Sponsor or Investigator* – applies to the situation where the entire study is terminated by the sponsor or investigator, or other regulatory authority for any reason.
2. *Withdrawal of consent* – applies to a subject who withdraws consent to participate in the study for any reason.
3. *Noncompliant with protocol* – applies to a subject who does not comply with protocol-specific visits or evaluations, on a consistent basis, such that adequate follow-up is not possible, and the subject's safety would be compromised by continuing in the trial. This also applies to a subject who is lost to follow-up and is not reachable by telephone or other means of communication and cannot be located.
4. *Completed follow up after developing an AE* – applies to a subject who is withdrawn from study due to an AE, serious or otherwise. Any grade 3 or greater AE that is assessed as possibly, probably, or definitely related to vaccination, PfSPZ Vaccine or placebo (other than local reactions lasting <72 hours, or systemic reactions lasting <48 hours) will result in withdrawal of the subject from further vaccinations. Subjects may also be withdrawn for any AE that would cause continued participation in the study to not be in the best interest of the subject, as per the investigator's judgment. Any subject who will not receive any further vaccination because of an AE related to study agent will be followed for safety until at least resolution of that AE and will be encouraged to remain in the safety evaluation for the duration of the study.
5. *Other* – is used when previous categories do not apply and a written explanation is required.

If a subject withdraws or is withdrawn prior to completion of the study, the reason for this decision will be recorded in the source documents and CRFs. Any subject who has received at least one dose of vaccine will be encouraged to remain in the safety evaluation for the duration of the study. The subject's data will be included in the safety and immunogenicity analysis. If a subject fails to complete all planned vaccinations because of an AE or SAE, the subject will be followed until resolution or stabilization of the event. If a subject withdraws, the investigator will make a reasonable effort to determine the reason.

11.13.1 Replacement of Withdrawn Subjects

Subjects who have received at least one vaccination and who withdraw or are terminated from the study prior to completion will not be replaced. In the main phase, subjects withdrawn before the first vaccination may be replaced.

11.14 Unblinding for the Study

Intentional, unscheduled unblinding may occur if a subject experiences a SAE that the treating clinician and/or site PI believes warrants unblinding to provide appropriate clinical management of the subject. The request for unblinding may be requested by the site PI or designee, sponsor, sponsor medical monitor, independent medical monitor, and DSMB. If non-emergent, all parties should be notified to discuss prior to unblinding taking place. If unblinding is requested, an "Unblinding Report" should be documented per standard operating procedures and submitted to the study statistician for formal unblinding.

If emergency unblinding is required, the PI or designee will contact the study statistician or study pharmacist for unblinding. The sponsor will be informed within one business day that the unblinding was necessary and a submitted "Unblinding Report" will be provided within 2 business days.

Subjects who are unblinded will be encouraged to remain in the study to be followed for safety.

For subjects who do not enroll in the booster phase, scheduled unblinding of the subject by the unblinded pharmacist will occur on Study Day 295 (*Arms 1 and 3a*) and Study Day 211 (*Arms 2 and 3b*) at the completion of the subject's final visit as already outlined in **Appendix A** per site procedures. For subjects enrolled in the booster phase, scheduled unblinding by the unblinded pharmacist will occur on Study Day 561 (*Arms 1 and 3a*) and Study Day 477 (*Arms 2 and 3b*). All primary and secondary endpoints will have been completed at this time. Individuals directly continuing AE assessment, including study investigators, or performing assays for exploratory endpoints will remain blinded to individual randomization until assessment or assays are completed.

11.15 Safety Oversight

11.15.1 Sponsor Medical Monitor

A medical monitor, representing the IND sponsor (Sanaria, Inc) has been appointed for oversight of safety in this clinical study. The sponsor medical monitor will be responsible for performing safety assessments.

11.15.2 Independent Safety Monitor (ISM) in Mali

An independent safety monitor (ISM) in Mali will review the study prior to initiation and will be available to advise the investigators on study-related medical issues and to act as a representative

for the welfare of the subjects. The ISM will conduct independent safety monitoring and recommend appropriate action regarding adverse events and other safety issues. The ISM is an expert in the field of oversight of clinical trials conducted in Mali and internal medicine, specifically in the population under study in Mali. The ISM does not have direct involvement in the conduct of the study and does not have other interests with any collaborating pharmaceutical firms or their competitors.

All serious adverse events, all UPs, and all FDA IND Safety Reports will be reported by the PI to the ISM prior to or at the same time they are submitted to the IRB or IND sponsor. The ISM will be notified immediately if any pausing rule is met and the ISM will provide recommendation for continuation, modification, or termination of the study. The PI will also notify the medical monitor if intentional or unintentional unblinding occurs.

11.15.3 Data and Safety Monitoring Board (DSMB)

As agreed with OCRPRO, for this study a DSMB chartered by the IND sponsor, Sanaria, Inc. will be used instead of the NIAID Intramural DSMB.

The DSMB will review the study prior to initiation and as outlined in [Figure 5](#) and [Section 11.7](#). The board may convene additional reviews as necessary, and will issue recommendations concerning continuation, modification, or termination of the study. All SAEs, UPs, and all IND Safety Reports will be reported by the sponsor to the DSMB.

The DSMB will review the study data to evaluate the safety, efficacy, study progress, and conduct of the study. The sponsor will notify the DSMB at the time pausing criteria are met and obtain a recommendation concerning continuation, modification, or termination of the study. The PI will submit written DSMB summary reports with recommendations to the IRB(s).

12 CLINICAL MONITORING

12.1 Site Monitoring Plan

As per International Conference on Harmonisation (ICH)-GCP 5.18 and FDA 21 CFR 312.50, clinical protocols are required to be adequately monitored by the study sponsor. This study monitoring will be conducted according to the “NIAID Intramural Clinical Monitoring Guidelines.” Monitors under contract to the NIAID/OCRPRO will visit the clinical research site to monitor aspects of the study in accordance with the appropriate regulations and the approved protocol. The objectives of a monitoring visit will be: 1) to verify the existence of signed informed consent documents and documentation of the informed consent process for each monitored subject; 2) to verify the prompt and accurate recording of all monitored data points, and prompt reporting of all SAEs; 3) to compare abstracted information with individual subjects’ records and source documents (subjects’ charts, laboratory analyses and test results, physicians’ progress notes, nurses’ notes, and any other relevant original subject information); and 4) to help ensure investigators are in compliance with the protocol. The monitors also will inspect the clinical site regulatory files to ensure that regulatory requirements: for the Office for Human Research Protections (OHRP), FDA, and applicable guidelines (ICH-GCP) are being followed. During the monitoring visits, the investigator (and/or designee) and other study personnel will be available to discuss the study progress and monitoring visit.

The investigator (and/or designee) will make study documents (e.g., consent forms) and pertinent hospital or clinical records readily available for inspection by the local IRB, the FDA,

the IND Sponsor (Sanaria), the site monitors, and the NIAID staff for confirmation of the study data.

A specific protocol monitoring plan will be discussed with the PI and study staff prior to enrollment. The plan will outline the frequency of monitoring visits based on such factors as study enrollment, data collection status and regulatory obligations.

13 STATISTICAL CONSIDERATIONS

13.1 Endpoints and Statistical Methods

13.1.1 Safety analysis

Safety will be assessed by line listing and tables at the individual level. Intention-to-treat (ITT) group comparisons, between the vaccine arms and the control arm, will be performed in terms of the proportions of solicited AE, related AE and SAE. Other concerning trends will be investigated as needed or requested by the PI, ISM, IND sponsor, and/or DSMB.

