1.7.1 Safety

Thus far, the vaccine regimen has been safe and well tolerated. There have been no serious adverse events (SAEs) or Grade 4 AEs. As expected, there are higher numbers of AEs in standard longer regimen *Arm* (*Arm 1/3a*) as this group has been enrolled and in follow up for a longer period of time than the condensed regimen *Arm* (*Arm 2/3b*). However, as demonstrated in **Table 4**, the proportions of AEs are similar between the two regimens indicating that administering PfSPZ Vaccine within a short period of time does not result in higher numbers of AEs compared to the standard longer regimen. All AEs were transient and have resolved without sequelae.

Grade 1 AEs

There have been 744 Grade 1 AEs to date. Lab abnormalities account for 153 (20.5% of total; 97 in *Arm 1/3a* and 56 in *Arm 2/3b*). The majority have been absolute neutrophil count decreases (30 in *Arm 1/3a*; 22 in *Arm 2/3b*), white blood cell count decreases (34 in *Arm 1/3a*; 23 in *Arm 2/3b*), and increased blood creatinine (20 in *Arm 1/3a*; 6 in *Arm 2/3b*). Most of the clinical AEs have been headache, injection site pain, malaria, and upper respiratory like illnesses.

Grade 2 AEs

There have been 71 total AEs to date (46 in *Arm 1/3a*; 25 in *Arm 2/3b*). Lab abnormalities account for 43 (60.5% of total; 29 in *Arm 1/3a* and 14 in *Arm 2/3b*). Of the 43 lab abnormalities, 23 have been from absolute neutrophil count decreases, with 16/23 occurring in *Arm 1/3a*, 5 were determined to be related to the study. 7 episodes have occurred in *Arm 2/3b*, 3 were determined to be related to the study. There have been 28 variable clinical AEs, most common being hypertension (4/17 in *Arm 1/3a*; 2/11 in *Arm 2/3b*) and malaria cases.

Grade 3 AEs

There have been 16 total AEs to date (10 in *Arm 1/3a*; 6 in *Arm 2/3b*). There was only 1 AE of decreased platelet count (in *Arm 1/3a*) thought possibly related to the vaccine due to timing. There was a total of 8 Grade 3 malaria AEs, 4 in each arm. These participants presented with Grade 3 fever but were otherwise in stable condition.

Table 4: Summary of AEs to date

	Arm 1/3a (n=105)	Arm 2/3b (n=105)	TOTAL
Clinical AEs			
Grade 1	397 (72%)	194 (69%)	591 (71%)
Grade 2	17 (3%)	11 (4%)	28 (3.4%)
Grade 3	9 (1.6%)	5 (1.8%)	16 (1.9%)
Lab abnormalities			
Grade 1	97 (18%)	56 (20%)	153 (18.4%)
Grade 2	29 (5.3%)	14 (5%)	43 (5.2%)
Grade 3	1 (0.2%)	1 (0.3%)	2 (0.2%)
TOTAL	550 (66%)	281 (34%)	831 (100%)

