4 STUDY ENDPOINTS

4.1 Primary Endpoints

Safety:

1. Incidence of local and systemic adverse events graded by severity occurring within 7 days after each vaccine administration. (Main phase).
2. Incidence of local and systemic adverse events (AEs) graded by severity occurring within 7 days after each vaccine administration (Booster phase).

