11.3 Investigator Assessment of Adverse Events

If a diagnosis is clinically evident (or subsequently determined), the diagnosis rather than the individual signs and symptoms or lab abnormalities will be recorded as the AE.

All solicited (see **Table 6** below) and unsolicited AEs will be recorded through Day 7 after each injection. Injection site reactions will be assessed until Day 7 after injection (PfSPZ Vaccine or normal saline) or until resolved.

After the periods specified above only unsolicited AEs, SAEs, UPs, and NOCIs will be recorded.

Table 6: Solicited Adverse Events

Laboratory adverse events¹	
Hemoglobin (decreased hemoglobin)	Platelet count (thrombocytopenia or thrombocytosis)
WBC (leukopenia or leukocytosis)	Creatinine (Cr) (increased Cr)
ANC (neutrophil count decreased) or AGC (granulocyte count decreased)	ALT (increased ALT)
Local reactogenicity (secondary to PfSPZ Vaccine/normal saline) – through Day 7 post injection	
Injection site pain/tenderness	Injection site induration
Injection site erythema/redness	Injection site swelling/edema
Injection site pruritus	Injection site bruising
Systemic reactogenicity (secondary to PfSPZ Vaccine/normal saline) – through Day 7 post injection	
Rash	Urticaria
Generalized pruritus	Generalized Edema
Headache	Fever or feverish
Chills	Malaise/Fatigue
Myalgia	Arthralgia
Sweats	Diarrhea
Back Pain	Chest Pain (non-musculoskeletal)
Nausea/Vomiting	Abdominal Pain

¹ Note absolute lymphocyte counts will be capture on CRFs for use for research assessments. If clinically significant changes as determined by PI, these may also be reported as AEs as noted below.

Any laboratory abnormalities (other than those specified as safety labs in the protocol as defined by the values in the toxicity table) should be reported as AEs if they require intervention. Interventions include, but are not limited to, discontinuation of treatment, dose reduction/delay, additional assessments, or concomitant treatment. In addition, any medically important laboratory abnormality may be reported as an adverse event at the discretion of the investigator. This could include a laboratory result for which there is no intervention, but the abnormal value suggests a disease or organ toxicity. In addition, similar to solicited AEs, all laboratory AEs as defined in **Appendix C**, will be collected and graded for severity through 7 days after each vaccination until resolved.

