11.3.2 Causality

Causality (likelihood that the event is related to the study agent) will be assessed considering the factors listed under the following categories:

Definitely Related

- reasonable temporal relationship
- follows a known response pattern
- clear evidence to suggest a causal relationship
- there is no alternative etiology

Probably Related

- reasonable temporal relationship
- follows a suspected response pattern (based on similar agents)
- no evidence of a more likely alternative etiology

Possibly Related

- reasonable temporal relationship
- little evidence for a more likely alternative etiology

Unlikely Related

- does not have a reasonable temporal relationship
OR
- good evidence for a more likely alternative etiology

Not Related

- does not have a temporal relationship
OR
- definitely due to an alternative etiology

Note: Other factors will also be considered for each causality category when appropriate. Causality assessment is based on available information at the time of the assessment of the AE. The investigator may revise the causality assessment as additional information becomes available.

The degree of certainty with which an AE can be attributed to administration of the study vaccine will be determined by how well the event can be understood in terms of one or more of the following:

- The event being temporally related with vaccination or reproduced on re-vaccination;
- A reaction of similar nature having previously been observed with this type of vaccine and/or formulation;
- The event having been reported in the literature for similar types of vaccines; and/or
- Whether or not there is another identifiable cause.

All local (injection site) reactions will be considered causally related to vaccination. All malaria cases will be reported as not related to vaccination unless results indicate otherwise.

Asymptomatic parasitemia (positive blood smears without related malaria clinical symptoms) will not be reported as an AE. Clinical malaria will be reported as an AE.

Reports will further classify AEs as follows:

- Related - all AEs that are assessed as definitely, probably, or possibly related.
- Unrelated - all AEs assessed as unlikely or definitely not related.

When reporting to regulatory authorities and IRBs is needed, AE relationship will be determined as noted above.

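### Section 13.1.1 pre-specifies no between-arm comparison of unsolicited AEs, Grade 3 AEs or clinical malaria regardless of causality, so late non-serious harms are compared only if a blinded investigator calls them related

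*Combined protocol and SAP*

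**What the plan says.** Section 13.1.1 has three parts. The display is non-comparative: "Safety will be assessed by line listing and tables at the individual level". The ITT comparison of vaccine with control "will be performed in terms of the proportions of solicited AE, related AE and SAE". Anything else is discretionary: "Other concerning trends will be investigated as needed or requested by the PI, ISM, IND sponsor, and/or DSMB". The section names no comparison of unsolicited AEs, of AEs by grade, or of AEs regardless of relationship.

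The primary endpoint in Section 4.1 covers a short window: "Incidence of local and systemic adverse events graded by severity occurring within 7 days after each vaccine administration". Recording goes on much longer. Section 11.3 states: "After the periods specified above only unsolicited AEs, SAEs, UPs, and NOCIs will be recorded". Section 3.1 puts follow-up at about six months after the third injection and again after the fourth.

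Section 11.3.2 makes clinical malaria an AE and sets its causality in advance: "All malaria cases will be reported as not related to vaccination unless results indicate otherwise". Malaria is not among the solicited terms in Table 6, and Section 11.3 has a diagnosis recorded in place of its symptoms. Section 13.1.2 compares arms on first positive blood smear.

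**The concern.** Safety is the only primary objective. After Day 7, an AE that is not an SAE reaches a pre-specified comparison only through a causality judgement made case by case under blinding. Randomised allocation could show whether such an event is more frequent on vaccine without anyone having to attribute single cases, and the planned analysis does not commit to using it for these events.

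At stake is how an unexpected late effect would be handled. It could be called unrelated in each individual, and then the pre-specified tables would show no excess of related AEs although data able to show the imbalance had been collected. The same applies to a change in the severity or recurrence of clinical malaria, where the causality label is fixed by default. A comparison chosen later, on request, carries less weight than one named beforehand.

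**Working it through.** **1. The plan's own safety figure (Section 13.2).** The probability of at least one AE among 70 subjects at a rate of 0.033 is 1 − (1 − 0.033)^70 = 0.9045, which reproduces the stated 90%. It describes seeing an event within one 70-subject arm. In a 35-subject control arm the same rate gives 1 − 0.967^35 = 0.691. The figure says nothing about comparing arms.

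**2. Grade 3 AEs to date (Section 1.7.1, Table 4).**
- Total: 10 in Arm 1/3a + 6 in Arm 2/3b = 16. Table 4 agrees by arm: (9 + 5) clinical + (1 + 1) laboratory = 16. Its total column shows 16 for clinical Grade 3 alone, where the arms add to 14; the 16 used here is clinical plus laboratory.
- Related: "There was only 1 AE of decreased platelet count (in *Arm 1/3a*) thought possibly related to the vaccine due to timing".
- Malaria: "There was a total of 8 Grade 3 malaria AEs, 4 in each arm".
- SAEs: none to date.

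Upper bound outside the comparisons: 16 − 1 = 15, and 15/16 = 93.8%. Lower bound: the 8 malaria events, which are not solicited terms, not SAEs and not described as related; 8/16 = 50%. The other 16 − 1 − 8 = 7 cannot be placed, because the text does not say whether they were solicited terms within 7 days. At least one is a laboratory AE, a type that Table 6 lists as solicited.

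**3. Clinical malaria after dose 3 (Table 5, vaccine and placebo pooled).** Episodes: 45 + 40 = 85. People: 35 + 36 = 71 of 101 + 103 = 204, or 34.8%. Smear-positive people: 53 + 51 = 104 of 204, or 51.0%. With no SAEs to date, none of the 85 episodes entered by the SAE route.

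**4. What an added comparison could show.** The documents state no alpha for safety; two-sided 0.05 is assumed. For Grade 3, the control rates are assumptions: 4%, and 7.6% (16/210, taking one event per person). Power by Fisher's exact test:

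| True ratio | Control rate | 70 v 35 | 140 v 70 |
|---|---|---|---|
| 2 | 4% | 5% | 13% |
| 2 | 7.6% | 13% | 30% |
| 3 | 4% | 18% | 43% |
| 3 | 7.6% | 46% | 81% |

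For clinical malaria, assuming 45% v 30%, power is 33% at 70 v 35 and 57% at 140 v 70. If both arms had the pooled 34.8%, the 95% half-width for the risk difference at 70 v 35 would be about 1.96 × √(0.348 × 0.652 × (1/70 + 1/35)) = 0.193, or 19 percentage points. The added tables would be descriptive.

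**The case against.** The strongest reply is that the plan is less closed than it looks. Section 13.1.1 lets the PI, safety monitor, sponsor or DSMB ask for other trends. Sections 11.7 and 11.15.3 have the DSMB review safety and efficacy data, and Section 7.2 allows for an unblinded closed session. A reader might infer that these events are never compared by arm. The documents do not support that; they support only that the comparison is not pre-specified. The discretionary clause names no event class or method, so that narrower point stands.

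A reader might also infer that only harms already suspected are compared. That is wrong: solicited AEs, including laboratory terms, and SAEs enter whatever their causality, and the 7-day primary endpoint has no causality filter. Nor do the documents show that delayed organ toxicity would be missed. Under Section 11.3.2 a possible relationship counts as related and may be revised later, and a medically important event is an SAE. It could be missed; no more can be said.

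Clinical malaria is not wholly uncompared. Its definition in Section 5.4.5 requires parasites, and smears are the diagnostic throughout. A person with smear-diagnosed malaria after dose 3 is therefore ordinarily also an event in the first-positive-smear analysis, so an excess of infection leading to malaria would be tested. Symptoms, grade and repeat episodes would not. The malaria default also has an exception where results indicate otherwise.

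Finally, power is low. That argues for estimates with intervals, not for leaving the tables out. The protocol's own background reports an earlier trial of this product that way: Table 3 sets all unsolicited AEs beside related ones by vaccine and placebo (31.7% v 33.3% of volunteers with any unsolicited AE).

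**Conclusion.** The point holds as a gap in pre-specification. Non-serious unsolicited AEs after Day 7 reach a planned between-arm comparison only through a blinded relatedness judgement. On the figures to date, 8 to 15 of 16 Grade 3 AEs (50% to 94%) lie outside the pre-specified comparisons. It is tempting to say that nearly all do, but that takes the upper bound as fact; the status of seven events is not given. For clinical malaria (85 episodes in 71 of 204 people), grade, symptoms and recurrence are compared only if a case is an SAE or is shown to be related.

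The range assumes that the Section 1.7.1 narrative is complete on which Grade 3 AEs were called related. Its counts pool vaccine and placebo, so they show how many events the plan leaves out and not whether any imbalance exists. No planned result is biased or invalidated. This is an improvement that should be made to the analysis of the primary objective.

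**What to change.** Amend Section 13.1.1 to add, for Arm 1 against Arm 3a and Arm 2 against Arm 3b, separately for the main and booster phases, the proportion of subjects with:
- any unsolicited AE;
- any Grade 3 or higher AE;
- clinical malaria, with worst grade and number of episodes tabulated.

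All should be counted regardless of assigned causality and over the full follow-up of the phase, and reported as risk differences with confidence intervals, stated to be descriptive. Keep the solicited, related and SAE comparisons.

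The cost is a wording change and a few tables from AE data already collected. The downside is more comparisons, some of which will look notable by chance, hence the descriptive reading. No dose, schedule, causality definition or other clinical rule needs to change.
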